4.6 Risk Assessment and Mitigation

Risk is scored as Probability (P: 1–3) × Severity (S: 1–3), yielding a risk grade of 1–2 (low), 3–4 (moderate), 5–6 (high), or 7–9 (very high). Ten risk categories are assessed, including training safety (elastic-band breakage, exercise-induced cardiovascular events, falls), adverse-event reporting delays, data privacy, protocol compliance, adherence decline, equipment/IT failures, public health emergencies, and budget constraints. Mitigation measures encompass branded-equipment inspections, baseline PAR-Q screening, continuous heart-rate monitoring, slip-resistant training surfaces, 24-hour SAE dual-channel reporting, AES-256 data encryption, gamified adherence incentives, 10% reserve equipment, contingency home-based training protocols, and 10% contingency budgets.

4.7 Ethical Approval

4.7.1 Ethics committee and approval status

Ethical approval is pending.

4.7.2 Informed consent process

Each candidate receives a plain-language informed consent document. Research staff provide oral, item-by-item explanations covering study purpose, procedures, risks (potential muscle soreness, minimal DXA radiation exposure), and benefits (free BMD reports, personalised exercise guidance). Participation is voluntary; withdrawal is permitted at any stage without consequence. Privacy protections (coded identification, no publication of individual data) are detailed. Following opportunity for questions and discussion, participants sign or fingerprint the consent form, witnessed and co-signed by the investigator.

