3.3.4 Detailed measurement schedule

表 3.3.4 Data measurement schedule 数据测量时间表						
Measurement field 测量领域	Specific measurement items 具体测量项目	T0	T1	T2	T3	备注
		Before intervention 干预前	4 months 4 个月	8 months 8 个月	14 months 14 个月	
Demography 人口学	Age, gender, education level, medical history, medication use	✓				Baseline collection only
Physical indicators	Height, weight, BMI	✓		✓	✓	Tracking changes

身体指标						
BMD 骨密度 DXA	Lumbar spine and hip BMD	✓	✓	✓	✓	4 months DXA As needed
Body functions 身体功能	SPPB Overall Rating	✓	✓	✓	✓	
	Overall balance	✓	✓	✓	✓	
	4-meter pace	✓	✓	✓	✓	
	5 Sit-to-Stand (5STS)	✓	✓	✓	✓	
	Grip strength (HGS)	✓	✓	✓	✓	Intermediary Indicators
Questionnaire 问卷调查	SF-36	✓	✓	✓	✓	
	FES-1	✓	✓	✓	✓	
	eHLQ、TAM	✓	✓	✓		Track
Implementation process 实施过程	Training compliance and dosage (platform log and manual log)		✓	✓		Continuous recording to stage nodes
Safety Monitoring 安全监测	Cumulative number of falls & adverse events			✓	✓	Summary
	New fracture				✓	
Behavior Tracking 行为追踪	Daily physical activity after intervention				✓	

Measurements are conducted at four time points: T0 (baseline, 1 week pre-randomisation) includes comprehensive demographic, clinical, functional, and questionnaire assessments; T1 (mid-intervention, 4 months) comprises streamlined assessments covering DXA (resources permitting), functional tests, adherence data, and questionnaires; T2 (end of intervention, 8 months) repeats the full baseline assessment battery plus cumulative adverse events; and T3 (follow-up, 20 months) evaluates long-term outcomes including new fractures, BMD maintenance, and post-intervention physical activity.

Chapter 4 Overall Methodology and Ethics

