		Precautions	
1. Do not hold your breath during training to prevent cardiovascular disease
 
2. When exercising, pay attention to inhaling when exerting force and exhaling when relaxing
 
3. After exercise, use the smart health bracelet to remind the elderly to fill in the exercise diary.

		
4. Before exercise, self-assess whether there are any discomfort symptoms, blood pressure and blood sugar control, and stop exercising if you feel uncomfortable
 
5. If the patient experiences dizziness, chest tightness, difficulty breathing and other discomfort symptoms during exercise, stop exercising immediately and contact the researcher immediately
 
6. Gradually increase the intensity of exercise to ensure patient tolerance.

Health Education Program	Expert Lectures	
1. Definition, classification and harm of the disease, etc., to make patients aware of the susceptibility of the disease
 
2. The effect of exercise on osteoporosis and the harm of inactivity, etc., to make patients aware of the benefits of exercise and the severity of inactivity
 
3. Analyze the patient's current movement disorders, gradually eliminate the obstacles they may encounter, and correct incorrect cognition

	1 offline group class per month	
1. Patients share their current feelings about exercise and the obstacles they encounter
 
2. Patients with strong exercise execution ability share their experiences
 
3. Review the effects of exercise
 
4. Provide supplementary health education

	Once a week, offline action guidance, error correction and adjustment	
1. Ask patients about their individual differences in the implementation of the plan
 
2. Encourage patients to keep exercising
 
3. Understand and guide patients on how to master exercise methods, and timely micro-control the amount of exercise
 
4. Export the patient's health data and exercise status analysis for this week through the smart bracelet data platform and use the data to make patients more confident to continue to persist.
 
5. Ask patients about their exercise status in the past week and encourage them to express their feelings about exercise.
 
6. Emphasize precautions during exercise to ensure patient safety

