Periodised progression follows dual-indicator control: volume progression (one additional set per exercise every 4 weeks, maximum 3 sets), intensity progression (resistance-band upgrade when RPE ≤ 4 with 15 standard repetitions), and density progression (inter-set rest reduced from 120 seconds to 75 seconds after week 12).

Smart components: each participant receives a Huawei Band 10 smart wristband that monitors heart rate, fall events, and blood pressure via Bluetooth synchronisation to the community health management platform. Training completion is recorded through WeChat-based manual check-in. A WeChat mini-programme delivers daily training prescriptions with illustrated guidance. The system includes automated training reminders and safety alerts (abnormal heart-rate detection triggers rest prompts and staff notification).

Personnel support: trained staff provide in-person guidance during the first week, with monthly on-site supervision thereafter. A designated team member contacts each participant weekly via WeChat to address questions and maintain adherence. Health education includes monthly group lectures and weekly one-on-one technique correction sessions.

Safety measures: pre-training medical screening (physical examination and exercise-risk assessment), individualised modifications for comorbidities (e.g., extended warm-up and blood-pressure monitoring for hypertensive patients), on-site emergency equipment (first-aid kit, AED), and a formal adverse-event reporting mechanism with monthly review and immediate reporting of serious events to the ethics committee.

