4.7.3 Data safety and monitoring

An internal safety monitoring mechanism is established: two senior physicians not directly involved in intervention delivery review trial operations and safety data every 4 months. Serious adverse events (e.g., training-related fractures, hospitalisation) trigger immediate review, participant suspension, and risk reassessment before deciding whether to modify or terminate the protocol.

References

- [2] CHEN, Y. (2024, FEBRUARY 19). *DI QI CI QUANGUO RENKOU PUCHA GONGBAO [THE 7TH NATIONAL POPULATION CENSUS BULLETIN]*. THE STATE COUNCIL OF THE PEOPLE'S REPUBLIC OF CHINA. [HTTPS://WWW.GOV.CN/GUOQING/2021-05/13/CONTENT_5606149.HTM](https://www.gov.cn/guoqing/2021-05/13/content_5606149.htm)
- [3] YIMING [佚名]. (2019). ZHONGGUO GUZHI SHUSONG ZHENG LIUXINGBINGXUE DIAOCHA JI "JIANKANG GUGE" ZHUANXIANG XINGDONG JIEGUO FABU [EPIDEMIOLOGICAL SURVEY OF OSTEOPOROSIS IN CHINA AND RESULTS OF THE "HEALTHY BONE" INITIATIVE]. *ZHONGHUA GUZHI SHUSONG HE GU KUANGYAN JIBING ZAZHI [CHINESE JOURNAL OF OSTEOPOROSIS AND BONE MINERAL RESEARCH]*, 12(4), 317–318.
- [5] KANIS, J. ASSESSMENT OF OSTEOPOROSIS AT THE PRIMARY HEALTH-CARE LEVEL. WHO SCIENTIFIC GROUP TECHNICAL REPORT. 2007.
- [7] NASO, C. M., LIN, Y., SONG, G., & XUE, H. (2025). TIME TREND ANALYSIS OF OSTEOPOROSIS PREVALENCE AMONG ADULTS 50 YEARS OF AGE AND OLDER IN THE USA, 2005–2018. *OSTEOPOROSIS INTERNATIONAL*, 36(3), 547. [HTTPS://DOI.ORG/10.1007/S00198-025-07395-3](https://doi.org/10.1007/s00198-025-07395-3)

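### The oral risk explanation in 4.7.2 lists only muscle soreness and DXA radiation and omits the training hazards named in 4.6 and 4.7.3

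*Protocol*

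**What the plan says.** Section 4.7.2 describes consent in two parts. The first is written: "Each candidate receives a plain-language informed consent document". The second is an oral explanation by research staff, given item by item. For that oral part the protocol states the content: "risks (potential muscle soreness, minimal DXA radiation exposure), and benefits (free BMD reports, personalised exercise guidance".

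The protocol describes what can go wrong in training in other places:

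- Section 4.6, the risk assessment, includes "training safety (elastic-band breakage, exercise-induced cardiovascular events, falls" among its assessed categories.
- Section 4.7.3, in the same ethics chapter as the consent text, says: "Serious adverse events (e.g., training-related fractures, hospitalisation) trigger immediate review, participant suspension, and risk reassessment".
- Section 4.3.1 tells participants: "If the patient experiences dizziness, chest tightness, difficulty breathing and other discomfort symptoms during exercise, stop exercising immediately". Its smart-system description adds that "abnormal heart-rate detection triggers rest prompts and staff notification".
- The schedule in section 3.3.4 has a safety row for "Cumulative number of falls & adverse events" and a separate row for new fractures.

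Section 4.7.1 states that ethics approval has not yet been obtained.

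**The concern.** An oral explanation that goes item by item should cover the foreseeable harms, and above all those the trial has planned for. Here the two mildest risks are in the consent text, and the ones that led to heart-rate alerts, slip-resistant surfaces, an on-site AED and a serious-adverse-event route are not.

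The population makes this more than a drafting matter. Section 4.2.1 admits people aged 60 or over with a T-score of -2.5 or below, or -2.0 or below with a previous fragility fracture, and section 4.3.1 has training progress to 70–80% 1RM. For such people falls and fracture bear directly on the decision to take part. Staff who follow 4.7.2 as written would not mention them in the oral explanation.

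What is at stake is the adequacy of the described consent process and agreement between sections that an ethics committee will read together. No statistical quantity depends on it.

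**Working it through.** No arithmetic applies beyond a count. The check sets the risks in 4.7.2 beside the hazards named elsewhere in the protocol.

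| Hazard | Where the protocol names it | In the 4.7.2 risk list? |
|---|---|---|
| Muscle soreness | 4.7.2 | Yes |
| DXA radiation | 4.7.2 | Yes |
| Elastic-band breakage | 4.6 | No |
| Exercise-induced cardiovascular events | 4.6 | No |
| Falls | 4.6; also counted in 3.3.4 | No |
| Training-related fracture | 4.7.3, as an example serious adverse event; new fractures also in 3.3.4 | No |

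The consent list has two risks. Four training hazards are named elsewhere, and 0 of those 4 appear in it. Hospitalisation, the other example in 4.7.3, is a consequence rather than a separate hazard, so it is not counted.

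Two details of reading matter.

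1. *Open or closed list.* The parenthesis in 4.7.2 carries no marker that its contents are examples. The protocol uses such a marker when it means one: 4.7.3 does so for serious adverse events, and 4.2.2 does so for other unsuitable conditions. The more natural reading is therefore that the two risks are the stated content.

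2. *Which section names what.* Fracture is not in the part of 4.6 that lists training-safety risks; it comes only from 4.7.3. Section 4.6 defines a probability-by-severity score but shows no score for any single item. So only training-related fracture is expressly labelled serious by the protocol. The other three are foreseen, but the text does not grade them.

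The heart-rate alert and the stop instruction in 4.3.1 confirm that cardiorespiratory trouble during exercise is anticipated. They belong to the delivery of the intervention, after enrolment, and do not stand in for what is explained before consent.

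**The case against.** The strongest objection is that the written consent document is not available to this review. It may name every one of these hazards, and going item by item may simply mean going through that document. A reader might infer from 4.7.2 that participants consent without being told of falls, fracture or cardiac events. The documents do not support that. They show what the protocol says the oral explanation covers, not all that participants receive. This part of the objection stands and sets the limit of the point. It does not remove the point: if the form is fuller, then the form and the protocol's account of the oral explanation disagree, and 4.7.2 still needs correcting.

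A second objection is that the parenthesis is a summary. The same sentence gives no detail on purpose or procedures and reduces benefits to two items. Section 4.6 is a project risk register that also covers IT failures and budget, and it is not offered as a disclosure list. This is fair, and the closed reading is not certain. But a summary that keeps only the minor risks is a poor guide for the staff who must deliver the explanation.

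A reader might also infer that poorly informed participants will under-report harm, because most sessions are unsupervised. The documents do not support this either. Section 4.3.1 tells participants to stop and contact the researcher for chest tightness, dizziness or breathing difficulty. It also provides wristband monitoring of heart rate and falls, weekly staff contact and monthly adverse-event review, and section 3.3.2 adds monthly fall diaries. Nor can a share of unsupervised sessions be fixed. Section 1.4.1 describes supervised training twice weekly. Section 4.3.1 gives three sessions per week, with in-person guidance in the first week, monthly on-site supervision after that, and weekly technique sessions. Those statements must first be reconciled.

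**Conclusion.** The point holds in a limited form. The oral risk explanation specified in 4.7.2 does not match the training hazards named in 4.6 and 4.7.3: none of the four appears in it. This is an inconsistency between current sections of the protocol, and it should be corrected before ethics approval.

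The conclusion rests on reading the 4.7.2 parenthesis as the intended content of the oral explanation, which its wording favours but does not prove. It makes no claim about the written form, about what participants actually know, or about the completeness of adverse-event reporting. It changes no sample size, endpoint, estimate or analysis.

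**What to change.** Replace the parenthesis in 4.7.2 so that the risks explained include falls, training-related fracture, exercise-induced cardiovascular events and elastic-band breakage, together with muscle soreness and DXA radiation. Then check the written consent document against the same list so that the oral and written parts agree with each other and with 4.6 and 4.7.3.

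Do not add a statement about how far sessions are supervised until sections 1.4.1 and 4.3.1 agree on frequency and supervision.

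The cost is about one sentence in the protocol and a check of one form while approval is pending. After approval the same change could need an amendment and renewed consent. The downside is possibly a few more refusals. Nothing in the training programme or in any clinical rule changes.

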4.1 Study Design Overview

4.1.1 Primary study design

This study employs a two-arm, parallel-group, assessor-blinded randomised controlled trial (RCT), with 1:1 allocation to the intervention and control groups. Outcome assessors are blinded to group assignment to minimise measurement bias. The protocol and reporting adhere to the CONSORT 2010 Statement, including transparent documentation of randomisation sequence generation, allocation concealment, blinding, and participant flow.

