4.2.3 Recruitment process

Recruitment proceeds through multiple community channels. The smart elderly care centre databases collectively cover 8,736 residents aged 60+, of whom 2,619 carry an OP diagnosis. Community sub-district offices co-host health seminars and post recruitment notices; community clinic physicians identify potentially eligible patients. Interested individuals undergo telephone pre-screening. Those preliminarily eligible attend an in-person enrolment assessment at the community centre, where they provide informed consent, undergo inclusion/exclusion verification, and complete baseline evaluations (DXA, functional tests, questionnaires). Eligible participants are then randomised via computer-generated random sequence. The entire process is documented in a CONSORT flow diagram.

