4.3.2 Control group

The control group receives standard health education without systematic RT. Activities include monthly 60-minute bone-health lectures (OP pathophysiology, nutritional guidance, fall-prevention strategies), delivered by hospital orthopaedic and community clinic staff, with

printed educational materials. Group discussion sessions are held every 4 months. Weekly telephone or WeChat follow-up by research staff provides general health advice (e.g., daily 20–30 minute walks), maintaining comparable contact frequency without introducing RT. This “attention control” design ensures that contact and engagement levels are balanced between groups.

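### Section 4.7.2 presents personalised exercise guidance as a benefit to every candidate without tying it to an arm, although the control arm does not receive it

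*Protocol*

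**What the plan says.** On consent, Protocol 4.7.2 states: "Each candidate receives a plain-language informed consent document". Staff then go through it orally, item by item. Among the items are "benefits (free BMD reports, personalised exercise guidance". The risks named in the same sentence are muscle soreness and a small DXA radiation dose. Neither the benefits nor the risks are assigned to an arm.

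On sequence and allocation, 4.2.3 places consent and baseline evaluation first: "Eligible participants are then randomised via computer-generated random sequence". Section 4.1.1 describes a two-arm parallel trial "with 1:1 allocation to the intervention and control groups".

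On the control arm, 4.3.2 says: "The control group receives standard health education without systematic RT". It provides monthly lectures, printed material, a group discussion every 4 months, and weekly telephone or WeChat contact that "provides general health advice (e.g., daily 20–30 minute walks), maintaining comparable contact frequency without introducing RT".

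On the intervention arm, 4.3.1 assigns elastic bands from a baseline functional assessment and sends daily training prescriptions. It adds: "Health education includes monthly group lectures and weekly one-on-one technique correction sessions".

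On blinding, 4.1.1 says only this: "Outcome assessors are blinded to group assignment to minimise measurement bias".

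**The concern.** Individual exercise guidance is what separates the two arms. Presenting it to everyone as a reason to take part describes the content of one arm as a benefit of the study, and it marks that arm as the desirable one before allocation is known.

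Three features of the design make this more than a matter of style.

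- Participants will know their arm, because only assessors are stated to be blinded.
- Two of the four measures listed as primary in 4.4.1, SF-36 PCS and MCS, are self-reported, as are the secondary FES-I and pain VAS in 4.4.2. Assessor blinding does not protect these.
- Exercise that controls start on their own would be hard to see during the 8-month comparison. The schedule in 3.3.4 ticks daily physical activity only at the final visit, and 3.3.3 names the IPAQ only as a baseline covariate.

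If controls expected guidance and did not get it, the possible effects are withdrawal (allowed at any stage under 4.7.2), self-started training, or lower self-ratings. They need not push the same way. Self-started training would dilute the BMD and SPPB differences. Disappointment would widen the SF-36 difference. Control withdrawal could bias either way.

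**Working it through.** The protocol gives no figure to reproduce on this point. It states no sample size, dropout rate or contamination rate. The check is a comparison of sections.

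1. **Who is told.** Each candidate (4.7.2), with no separate text by arm.
2. **When.** Before randomisation (4.2.3), so nobody yet knows which arm they will join.
3. **What they are told.** Free BMD reports and personalised exercise guidance (4.7.2), with no condition on allocation.
4. **Share allocated to control.** Under 1:1 allocation (4.1.1), 1/(1 + 1) = one half.
5. **Is the benefit delivered in each arm?**

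| Item | Intervention (4.3.1) | Control (4.3.2) |
|---|---|---|
| BMD measurement | Yes (schedule in 3.3.4) | Yes (schedule in 3.3.4) |
| Bone-health education | Monthly lectures | Monthly lectures, printed material |
| Individual exercise prescription | Daily, with bands matched to baseline function | None |
| One-to-one technique correction | Weekly | None |
| Exercise advice | Personalised | General, for example a daily walk |

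Free BMD reports and education can truthfully be offered to everyone. Personalised exercise guidance can be offered only to the intervention arm. The nearest control-arm element is the weekly contact, and the protocol itself describes its content as general.

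6. **Is it given to controls later?** No section offers controls the training or individual guidance after follow-up.
7. **Does the risk side show the same pattern?** Yes. Muscle soreness is essentially a risk of the training arm and is also listed without an arm. The sentence pools both arms for risks as well as benefits.

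Steps 1 to 6 establish the mismatch from the protocol's own text. Any effect on outcomes is a further inference, for which the documents provide no rate.

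**The case against.** The strongest reply is that 4.7.2 is a one-sentence list of topics, not the consent form. It pools risks and benefits over the whole study, as the unassigned muscle soreness shows. Candidates also receive a written document and an explanation of purpose and procedures, where random allocation and the content of the two arms would normally appear. That form is not among the pages available. This stands as a limit: it cannot be said that candidates will in fact be misled, or that controls were promised guidance. It does not remove the mismatch, because 4.7.2 sets out what staff must cover and gives the benefit without qualification.

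A second reply is that 4.3.2 is an attention-control design meant to balance contact and engagement. That counts in part. Weekly contact may limit disengagement, but general walking advice is not personalised guidance.

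A reader might go further and infer a definite inflation of false positives on the SF-36. For example, take an SD of 10, 48 participants per arm and a 2-point lower self-rating in controls. The standard error is 10 × √(2/48) = 2.04, and a two-sided 5% test would reject about 17% of the time with no effect of training. The arithmetic is right, but the SD, the sample size and the shift are all assumed, and none of the shift can be assigned to this sentence. In any open trial of training against education, properly informed candidates know that one arm trains and the other does not. Much of the disappointment or self-started exercise would therefore remain after the wording is corrected. What matters is the increment due to the wording, and the documents give no basis for that.

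**Conclusion.** The point holds as a mismatch between the consent summary and the arms. Section 4.7.2 presents to all candidates a benefit that 4.3.1 gives to one arm and 4.3.2 does not give to the other, which receives half of those randomised. Because participants know their arm and PCS and MCS are self-reported primary outcomes, the wording may add to control withdrawal, self-started exercise or lower self-ratings. The size of that addition is unknown, and the directions differ by endpoint.

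A reader might also infer that the SF-36 comparison is already compromised, or that control dropout is to be expected. The documents support neither: they give no rates, the consent form is not shown, and part of the risk comes from the open design itself. The case for correction rests on the accuracy of the consent information and the low cost of getting it right. It assumes that the consent form follows 4.7.2 as written. If the form already separates the arms, only the protocol text needs to be aligned with it.

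**What to change.** In 4.7.2:

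- List as common to all only free BMD reports and bone-health education.
- State the remaining benefits by arm, with individual exercise guidance under the training programme only.
- Assign the risk of muscle soreness to the training programme in the same way.
- Say that candidates have an equal chance of either programme and that individual exercise guidance belongs to one of them.

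Check that the consent form carries the same wording. Candidates who would not accept the control arm can then decline before randomisation, where their loss does not disturb the comparison, and not withdraw after it.

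The cost is a few sentences. Section 4.7.1 records ethics approval as pending, so the text can be corrected before approval. Allocation, outcomes and analysis are unchanged. Offering controls the training manual after their last visit would be a courtesy that the sponsor may consider. It is optional, and its absence is not part of the error.
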